11.0 EVALUATION DURING TREATMENT/INTERVENTION

MEASURE/TEST	Time to complete	Intervention Sessions (ERT-C or CBT-C) ^a	T2 (1-wk post last ERT-C or CBT-C) ^{b, e}	T3 (3-mos post ERT-C or CBT-C) ^e		T4 (6-mos post ERT-C or CBT-C) ^e
				Caregiver	Pt	
		Caregiver Only	Caregiver Only	Caregiver	Pt	Caregiver Only
Distress Thermometer (DT)	2 min	X	X	X		X
Hospital Anxiety and Depression Scale (HADS)	5 min	X	X	X		X
Penn State Worry Questionnaire (PSWQ)	5 min		X	X		X
Rumination-Reflection Questionnaire, Rumination subscale (RRQ-R)	5 min		X	X		X
Attentional Control Scale (ACS)	5 min	X	X	X		X
Experiences Questionnaire, Decentering subscale (EQ-D)	5 min	X	X	X		X
Emotion Regulation Questionnaire, Reappraisal subscale (ERQ-R)	3 min	X	X	X		X

Caregiver Quality of Life Index-Cancer (CQOLC) ^f	5 min		X	X		X
Caregiver Reaction Assessment (CRA) ^f	5 min		X	X		X
Self-Administered Comorbidity Questionnaire (SCQ)	5 min		X	X		X
Patient-Reported Outcomes Measurement Information System Global Health Scale (PROMIS-GH)	4 min		X	X	X	X
Credibility and Expectancy Questionnaire (CEQ)	2 min		X			
EORTC QLQ-C30	3 min				X	
Perceived Stress Scale (PSS)	4 min				X	
National Survey on Drug Use and Health (NSDUH), Healthcare Utilization	2 min				X	
Working Alliance Inventory-Short Form (WAI-SF)	8 min	X ^c				
COPE, Active Coping Subscale	2 min.	X				
Inflammatory Markers Assessment	5 min		X	X		X
Diurnal Cortisol Assessment	2 min. 4x a day over 3 days		X ^d	X		X
Total Time		22 min	80 min	78 min	13 min	78 min

^a ERT-C or CBT-C will be delivered over 8 individual sessions by a trained study therapist. The 8 sessions must be completed within 8 to 16 weeks from initiation of the first session. ^b Questionnaires at T2 should be completed on the same day as the last session, but may be completed within 1 week. ^c The Working Alliance Inventory will be administered after the fourth intervention session. ^d Saliva collection at T2 should begin the day after the last session. ^e Training case participants will not be asked to complete follow-up assessments. ^f Bereaved caregivers who report their loved one passing away will not be asked to complete these assessments.

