14.0 BIOSTATISTICS

This study is a psychotherapy RCT implemented at 2 clinical sites, with a 1:1 allocation of ERT-C to CBT-C. We propose to enroll 240 caregivers into either ERT-C or CBT-C. Caregiver participants will be assessed at pre-intervention (T1), post-intervention (T2), and at 3-months (T3) and 6-months (T4) follow-up for primary outcomes and mid-intervention at weekly therapeutic sessions for mechanistic measures and the HADS depression and anxiety outcomes. Up to 240 patients (for whom the caregiver is enrolled) will complete a short battery of assessments at T1 and T3. The four primary outcomes include caregiver depression, anxiety, worry, and rumination. Secondary outcomes include other caregiver and patient psychosocial and QOL measures. The primary analytic approach to testing the treatment efficacy in Aim 1 and change in biomarkers in Aim 3 will be Generalized Linear Mixed-Effects Model (GLIMMIX¹⁹¹), also known as Hierarchical Linear Model (HLM¹⁹²). For Aim 2, we will use an analytic strategy known as parallel process latent growth curve modeling (PP-LGCM), which is similar to a combination of growth curve models with the Baron and Kenney¹⁹³ approach, to test mediation of ERT-C on anxiety and depression via emotion regulation skills. PP-LGCM allows tests of both direct and indirect effects of treatment on outcomes through hypothesized pathways.

The statistics for the aims are described as follows:

AIM 1: Immediate and Longer-Term Efficacy of ERT-C vs. CBT-C in Improving Symptoms of Anxiety, Depression, Rumination and Worry.

Treatment-related improvements in anxiety, depression, worry and rumination symptoms (primary outcomes) and caregiver quality of life and burden (secondary outcomes) will be assessed by comparing measures at baseline, post-treatment, and at 3- and 6-months follow-up between ERT-C and CBT-C.

Hypothesis 1a: ERT-C will result in greater improvement in caregiver primary (i.e., anxiety and depression, worry, rumination) and secondary (i.e., QOL and burden) outcomes and these gains will be maintained at 6-months follow-up.

Hypothesis 1b: ERT-C will lead to greater improvements in cancer patient outcomes as compared to CBT at 3-months follow-up.

Exploratory Hypothesis 1c: Assess putative moderators of the efficacy of ERT-C versus CBT-C.

Primary Analyses:

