We will test differential effects of ERT-C versus CBT-C using separate GLIMMIX/HLM for each outcome (e.g., depression, anxiety). For HADS outcomes and for rumination and worry post-intervention outcomes, the *i*th caregiver, within the *j*th site, at the *k*th timepoint will be regressed on a time variable, an indicator for ERT-C arm, and time-by-arm interaction. That is, baseline assessments will be included as an outcome and not a covariate. This flexible analytic strategy will allow testing of non-linear time effects, treatment differences immediately post-treatment, and comparison of 6-month maintenance, all within the same model framework via specific contrasts. This strategy also utilizes all complete assessments, such that caregivers who miss data at a subset

of time points will still be included and analyzed in the model. Random per-caregiver and per-site intercepts will control for intraclass correlation introduced by repeated measures and cluster effects, which is an important statistical consideration in choosing GLIMMIX/HLM as our primary statistical approach. Prior to regression modeling, transformations to the outcome will be made as necessary and based on tests of parametric assumptions. A significant finding on the test of the interaction term would be evidence that there is a differential reduction in the outcome by treatment assignment. For immediate gains, data will be restricted to T1 to T2 (including the mid-intervention assessments for HADS outcomes). For 6-month maintenance, a similar model will be used, restricted to the post-intervention data. For HADS outcomes pre to post intervention, 10 assessments (T1, T2, and 8 mid-intervention timepoints) are expected; for all 4 primary outcomes, 3 timepoint assessments (T2, T3, T4) are expected for 6-month maintenance. A significant finding on the main time effect would indicate a change in outcomes during the 6-month follow-up for CBT-C participants, and a significant finding on the interaction coefficient would indicate a significantly different change in follow-up outcomes between ERT-C and CBT-C. Superiority is defined by a significant finding on post-treatment difference (T1 to T2) and either further significant differentiation post-intervention (T3 to T5) or no statistically significant differentiation if the CBT-C group converges with the ERT-C group during this time.

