Power and Sample Size for Aim 1. Preliminary data found ERT-C to have a pre-treatment to post-treatment effect size of $g=0.49$ on depression and anxiety. A recent meta-analysis found very small ($g=0.08$) effects of CBT on these outcomes; this implicates a differential effect size of $d=0.41$. Using an HLM model with up to 3 time points, a within-subject ICC of 0.2, allowing for approximately 20% attrition, and setting Type I error to the conservative value of 0.0125 to account for 4 primary outcomes, we simulate 90.4% power for the differential pre-treatment to post-treatment changes for Aim 1 if the effect size is at least $g=0.41$ and 82.8% power for a more conservative effect of $g=0.37$. Power was simulated using the *simr* [199] package in R. For patient outcomes, the PI anticipates at least 50% enrollment of patients associated to the caregivers, and comparable attrition between patients and caregivers. Enrollment of 120 patients, with 80% retention at the 3-month follow-up assessment will provide 80% power to detect a standardized effect of at least $d=0.63$ for the difference in change scores using an independent samples t-test approximation at alpha of 0.05. Similarly for rumination and worry from pre to post intervention, enrollment of 240 caregivers with 10% attrition during intervention will provide 80% power to detect a medium effect of at least $d=0.50$ with alpha of 0.0125 for these two primary outcomes.

AIM 2: Attention and Metacognitive Regulation Will Have Indirect Effects on the Primary and Secondary Outcomes. Growth curve models will assess overall effects of treatment on primary and secondary outcomes, and the partial mediation of primary outcomes via attention and metacognition regulation skills increases and whether this effect will be more pronounced in ERT-C compared to CBT-C.

Hypothesis 2a: Only skills that specifically target components of distress (i.e., attention regulation, metacognitive regulation) will mediate primary and secondary caregiver outcomes compared to other facets of improving the caregiving experience (i.e., reducing perceived burden, maladaptive behavioral coping).

Hypothesis 2b: These gains and mediation in attention and metacognitive regulation will be more pronounced in caregivers receiving ERT-C as compared to CBT-C.

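### The HADS pre-post time-by-arm test over 10 assessments names random intercepts only, so its nominal 1.25% level is exceeded if caregivers' slopes vary or nearby scores are serially correlated

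*Combined protocol and SAP*

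**What the plan says.** Section 14.0, Aim 1 Primary Analyses, fits a separate mixed model to each outcome, "regressed on a time variable, an indicator for ERT-C arm, and time-by-arm interaction", with baseline treated as an outcome. The inference is drawn from that interaction: "A significant finding on the test of the interaction term would be evidence that there is a differential reduction in the outcome".

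For the two HADS subscales the pre-post model is long: "For HADS outcomes pre to post intervention, 10 assessments (T1, T2, and 8 mid-intervention timepoints) are expected". The covariance is described in one sentence: "Random per-caregiver and per-site intercepts will control for intraclass correlation introduced by repeated measures and cluster effects". Aim 1 mentions no random slope, no serial or unstructured residual covariance and no robust standard error. The section does call the strategy flexible, but that refers to non-linear time and contrasts, which belong to the mean model.

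The power paragraph fixes the level for each primary outcome, "setting Type I error to the conservative value of 0.0125 to account for 4 primary outcomes", and uses a within-subject ICC of 0.2. Section 13.1 declares ERT-C superior if at least one of the four primary tests is significant.

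Two other places bear on the covariance. The Aim 2 model in Section 14.0 gives the outcome its own latent slope. Section 11.0 says of T2: "Questionnaires at T2 should be completed on the same day as the last session, but may be completed within 1 week". HADS is also completed before each session on the session day (Sections 4.1 and 11.0).

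**The concern.** The tested term is a difference between arms in mean within-caregiver slope. A random intercept removes differences in caregivers' overall level and does nothing for differences in their rate of change. Real slope variation is then treated as independent residual noise spread over 10 scores per caregiver, and the standard error of the interaction comes out too small. Positive serial correlation has the same effect.

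The plan gives reasons to expect both departures. Aim 2 models individual outcome trajectories, and the moderator analyses presume that response differs between caregivers. The pre-session-8 HADS and the T2 HADS can fall on the same day, whereas T1 and T2 are separated by a treatment course of 8 to 16 weeks.

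This is the confirmatory test for two of the four primary outcomes. Because one significant result suffices under Section 13.1, family-wise control depends on each test holding 0.0125. If, for illustration, both HADS tests ran at 5%, the Bonferroni bound would be 0.05 + 0.05 + 0.0125 + 0.0125 = 12.5% instead of 5%. Correlation between outcomes would make the actual rate lower than this bound.

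**Working it through.** **Plan's own figures.** The level reproduces: 0.05/4 = 0.0125. Sidedness is not stated; two-sided is assumed, so z = 2.498. The stated power (90.4% at g = 0.41, 82.8% at g = 0.37) could not be reproduced. With 96 per arm, a T1–T2 change on the total-SD scale at ICC 0.2 gives 40.1%/31.9%. The closest slope version (three points, effect per time unit, residual variance 1) gives 93.6%/87.0%. The simulation's time coding, residual SD and dropout pattern are not given, so this does not show the stated power to be wrong. It plays no part in what follows.

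**Inputs from the documents.** 240 caregivers ("We propose to enroll 240 caregivers into either ERT-C or CBT-C"), "with a 1:1 allocation of ERT-C to CBT-C"; 10 HADS assessments; intercept-only random effects; level 0.0125.

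**Assumptions.** Equally spaced points; complete data; baseline variance 1, of which ICC is between-caregiver and σ² = 1 − ICC is residual; SD of true T1–T2 change s = 0.3, 0.5 or 1.0 baseline SD; ICC 0.2, 0.5 or 0.7. Only ICC 0.2 comes from the plan.

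**Linear time.** For m points coded 0 to m − 1, the slope SD is s/(m − 1). Let r = [s/(m − 1)]² × Sxx / σ². The true variance of the interaction divided by the variance the model reports is

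R = (1 + r) / (1 + r/(m − 1)),

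and the actual level is 2[1 − Φ(2.498/√R)]. R does not depend on sample size. For m = 10, Sxx = 82.5, so r = 1.0185 s²/(1 − ICC).

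Example, s = 0.5 and ICC 0.2: r = 0.2546/0.8 = 0.318; R = 1.318/1.035 = 1.273; √R = 1.128; 2.498/1.128 = 2.214; level 2.7%.

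**Categorical time, T2–T1 contrast.** R = (s² + 2σ²) / [2σ²(1 + r/9)].

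**Three follow-up visits, T2–T4, linear time.** m = 3, Sxx = 2, with s now the SD of true T2–T4 change: r = 0.5 s²/(1 − ICC), R = (1 + r)/(1 + r/2).

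| s | ICC | √R, linear, 10 points | Level, linear, 10 points | Level, T2–T1 contrast | Level, T2–T4, 3 points |
|---|---|---|---|---|---|
| 0.3 | 0.2 | 1.05 | 1.7% | 1.4% | 1.4% |
| 0.3 | 0.5 | 1.08 | 2.0% | 1.6% | 1.5% |
| 0.3 | 0.7 | 1.12 | 2.6% | 1.8% | 1.6% |
| 0.5 | 0.2 | 1.13 | 2.7% | 1.8% | 1.6% |
| 0.5 | 0.5 | 1.20 | 3.7% | 2.2% | 1.8% |
| 0.5 | 0.7 | 1.30 | 5.5% | 2.8% | 2.1% |
| 1.0 | 0.2 | 1.41 | 7.7% | 3.6% | 2.5% |
| 1.0 | 0.5 | 1.57 | 11.2% | 5.1% | 3.0% |
| 1.0 | 0.7 | 1.79 | 16.2% | 7.3% | 3.8% |

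√R is the factor by which the reported standard error is too small.

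**Serial correlation alone (AR(1), no slope variation).** Linear slope: 2.1%, 3.4%, 5.1% and 10.0% at ρ = 0.1, 0.2, 0.3 and 0.5. T2–T1 contrast: 1.5% at ρ = 0.2 and 2.3% at ρ = 0.5.

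**Two occasions.** With m = 2, R = (1 + r)/(1 + r) = 1, so there is no inflation.

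**Simulation check** (linear time, 108 per arm, 8,000 trials per setting). The random-intercept test rejected in 1.2–1.5% of trials with neither departure. It rejected in 2.8% (ICC 0.5, s = 0.43), 10.5% (ICC 0.5, s = 0.93), 3.5% (AR(1) 0.2) and 10.0% (AR(1) 0.5). A test on per-caregiver slopes, applied to the same data, rejected in 1.1–1.5% throughout.

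**The case against.** The strongest reply is that no document states a slope variance or serial correlation for HADS. A reader might infer that the test simply runs at 3–10%. The documents do not support that: it is one slice of a range that starts at 1.25%. At the plan's own ICC of 0.2, stable differences between caregivers have SD √0.2 = 0.45. A true-change SD of that size gives only 2.4%, and reaching 10% would need a change SD of 1.17. This stands, and it is why the size is given conditionally.

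Second, the time coding is not fixed. Section 14.0 allows non-linear time and defines superiority on the T1-to-T2 difference, and on that reading the inflation is smaller. This also stands as to size. The single interaction term favours a linear reading, however, and the contrast is still above nominal under every departure examined.

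Third, because Aim 3 reuses the Aim 1 framework, a reader might extend the point to the T1–T2 biomarker model. That does not follow. With two complete occasions, the random-intercept interaction test is a comparison of change scores, which already absorbs slope variation.

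Fourth, the calculation uses equal spacing, while sessions run over 8 to 16 weeks and session 8 may coincide with T2. The exact figures would shift. The direction of the error would not.

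**Conclusion.** The concern holds in conditional form. Followed as written, the HADS T1–T2 analysis has a standard error that is too small whenever caregivers' true slopes differ or scores are positively serially correlated. The plan's own growth model allows the first, and its assessment schedule makes the second likely.

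Under the stated assumptions the nominal 1.25% level becomes:

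- linear time: about 1.7–5.5% for a true-change SD of 0.3–0.5, and 7.7–16% for 1.0;
- linear time with AR(1) of 0.2–0.5 alone: 3.4–10%;
- T2–T1 contrast: about 1.4–5%, or 7.3% at ICC 0.7 with SD 1.0, and 1.5–2.3% for AR(1) alone;
- three-visit follow-up model: about 1.4–3.8%.

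More recruitment would not help, because the variance ratio does not depend on sample size. The documents do not establish any one of these values as the true error rate.

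**What to change.** For the HADS T1–T2 models, pre-specify a caregiver random intercept and a random slope on time. Add a serial residual structure or robust standard errors to cover serial correlation, and use Kenward-Roger degrees of freedom where standard errors are model-based. State how time is coded, given that session spacing varies, and name the T2 arm contrast as the primary estimate. An unstructured covariance over all 10 occasions is less attractive: it has 10 × 11/2 = 55 parameters and suits irregular session dates poorly.

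For the T2–T4 models, specify a suitable covariance, for example unstructured over the three visits. The T1–T2 biomarker model needs no change on this account.

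The cost is a few sentences in Section 14.0, to be settled before the database is locked; no new data or participants are needed. Intervals become wider by roughly the √R factors above where the departures are real, and HADS power falls somewhat. The power loss cannot be quantified from the documents, so the power simulation should be rerun under the revised model with its inputs stated. If both departures prove negligible, little is lost.

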10.0 TREATMENT/INTERVENTION PLAN

Caregivers will be randomized to ERT-C or CBT-C and will meet with the therapist one-on-one via telepsychiatry for 8 individual sessions to be completed within 8 to 16 weeks from initiation of the first session. Telepsychiatry will be conducted through a platform approved by each site's respective Privacy Board (e.g. Webex, Zoom, Teams). Caregivers and patients will complete study assessments as per the schedule of assessments in Section 11.0. Caregivers who wish to discontinue treatment before completing all 8 sessions will be given the option to remain on study to complete follow-up assessments. Those who are not interested will be withdrawn from the study and will not complete follow-up assessments. Reasons for caregiver withdrawal will be documented. Please see Section 4.2 for a full description of the study intervention, including descriptions of the ERT-C and CBT-C treatment, training and supervision of study therapists, and ensuring fidelity to intervention.

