13.2 Criteria for Study Endpoint Evaluability

Participants need to only complete the baseline assessment for the data to be considered evaluable. If any caregiver participant withdraws consent prior to baseline assessment, they will be replaced.

Caregiver outcomes include treatment-related improvements in anxiety and depression symptoms, including worry and rumination(primary outcomes) and caregiver QOL and burden (secondary outcomes).

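### The 6-month maintenance model is cut to T2-T4, so caregivers who leave the study before T2 and all baseline scores are absent from it; one T1-T4 model with an unstructured covariance would keep them

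*Combined protocol and SAP*

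**What the plan says.** Section 14.0 (Aim 1, Primary Analyses) sets up a mixed model with time, arm and time-by-arm, and with random intercepts per caregiver and per site. It says "baseline assessments will be included as an outcome and not a covariate", and that the approach allows "comparison of 6-month maintenance, all within the same model framework via specific contrasts". The same paragraph then divides the data. For the first question, "For immediate gains, data will be restricted to T1 to T2 (including the mid-intervention assessments for HADS outcomes"). For the second, "For 6-month maintenance, a similar model will be used, restricted to the post-intervention data", and "for all 4 primary outcomes, 3 timepoint assessments (T2, T3, T4) are expected for 6-month maintenance". The maintenance terms it interprets are the time effect in CBT-C and the arm-by-time interaction.

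Three other places bear on who is in that model:

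- Section 13.2: "Participants need to only complete the baseline assessment for the data to be considered evaluable".
- Section 10.0: caregivers who stop therapy may stay for follow-up. Of the rest it says "Those who are not interested will be withdrawn from the study and will not complete follow-up assessments".
- Section 14.0, Attrition and Missing Data: missingness will be compared between arms and by pre-intervention measures. No imputation or sensitivity analysis is described.

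**The concern.** Baseline enters the model only as an outcome row, so restricting the data to T2-T4 removes it altogether. A caregiver who leaves the study before T2 then contributes nothing to the maintenance analysis, although Section 13.2 counts that caregiver as evaluable and a T1 score (and perhaps weekly HADS scores) is on file. Who remains is settled after randomization.

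Maintenance is part of Hypothesis 1a and of the definition of superiority in Section 14.0. If dropout during therapy relates to distress in one way under ERT-C and in another under CBT-C, the T2-T4 data cannot adjust for it, because the variable that would explain the dropout has been left out. The two restricted analyses also leave a gap: one ends at T2 and the other starts there, so neither estimates the arm difference from baseline to 6 months. The exploratory moderator models do use change scores at T4, but each includes a moderator interaction and needs an observed T4.

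**Working it through.** **Caregivers with no row.** The plan states no sample size or power for the maintenance model, so there is no figure to reproduce. From Section 14.0: N = 240, 10% attrition during intervention, 20% overall.

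- 240 × 0.10 = 24 absent, leaving 216 (108 per arm).
- 240 × 0.20 = 48 absent, leaving 192 (96 per arm), if the whole allowance fell before T2.

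**Size of the possible bias.** Input from the plan: a true arm difference of -0.41 SD, taken here as constant from T2 to T4. Assumptions not in the documents:

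- SD is 1 at each visit; the T1-T2 and T2-T4 correlations are 0.6; the T1-T4 correlation r14 is 0.3, 0.4 or 0.6.
- Dropout before T2 is logistic in T1, with an intercept of log(0.1/0.9) or log(0.2/0.8). The log-odds per SD are 0.7 in ERT-C and 0 in CBT-C (one arm), or 0.7 and -0.5 (opposite).
- There is no further loss after T2.

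Let D be the mean T1 among retained ERT-C caregivers minus that among retained CBT-C caregivers (0 before dropout). With T2-T4 data only:

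- bias in the T4 arm difference = r14 × D
- bias in the T2-T4 arm-by-time term = (r14 - r12) × D

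Numerical integration gives:

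| Loss before T2 | Pattern | D | T4 bias, r14 = 0.3 to 0.6 | Arm-by-time bias, r14 = 0.3 / 0.4 / 0.6 |
|---|---|---|---|---|
| about 11% | one arm | -0.078 | -0.023 to -0.047 | 0.023 / 0.016 / 0 |
| about 11% | opposite | -0.131 | -0.039 to -0.079 | 0.039 / 0.026 / 0 |
| about 21% | one arm | -0.143 | -0.043 to -0.086 | 0.043 / 0.029 / 0 |
| about 22% | opposite | -0.244 | -0.073 to -0.147 | 0.073 / 0.049 / 0 |
| either | same in both arms | 0 | 0 | 0 |

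In the fourth row with r14 = 0.3, the T2 difference is -0.41 + 0.6 × (-0.244) = -0.556 and the T4 difference is -0.41 + 0.3 × (-0.244) = -0.483. A constant effect therefore looks like partial convergence of 0.073 SD. Reversing the dropout pattern reverses the sign.

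**Scale.** With a T2-T4 correlation of 0.6, the SE of the arm-by-time term is √[2(1 - 0.6)] × √(2/n). That is 0.894 × √(2/108) = 0.122 at 108 per arm and 0.894 × √(2/96) = 0.129 at 96. The largest biases are then 0.039/0.122 = 0.32 SE and 0.073/0.129 = 0.57 SE.

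**Does adding T1 cure it?** That depends on the covariance. Under a random caregiver intercept with common correlation ρ, the likelihood estimate of each arm's mean at visit k is the retained mean plus ρ × (overall T1 mean - retained T1 mean). The remaining bias in the arm difference at visit k is (r1k - ρ) × D.

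- T2-T4 contrast: (r14 - ρ)D - (r12 - ρ)D = (r14 - r12)D. ρ cancels, so the bias stays at 0.073.
- T4 difference: large-sample fits, with assumed correlations involving T3 of 0.4 to 0.7, gave ρ of about 0.53 to 0.57. At 0.55 the result is -0.41 + (0.3 - 0.55) × (-0.244) = -0.35. The error changes sign and is almost as large as before.
- Unstructured covariance: ρ is replaced by the actual r1k, so both biases vanish. The fits returned about -0.41 and 0.00.

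**The case against.** The strongest reply is that maintenance is by nature a T2-T4 question, and that the randomized comparison sits in the T1-T2 analysis, which uses baseline (and weekly HADS for the HADS outcomes) and which superiority requires first. On this view "comparison of 6-month maintenance, all within the same model framework via specific contrasts" means only the same class of model, and Section 13.2 does not promise that every evaluable caregiver enters every model. The planned comparison of attrition by arm and by pre-intervention measures would also show whether selective dropout occurred.

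Much of this stands. A reader might infer several stronger things that the documents do not support:

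- That everyone who stops therapy is lost. Section 10.0 lets such caregivers stay in follow-up, and Section 14.0 keeps anyone with T3 or T4 even if T2 is missed.
- That baseline is discarded from the trial. It is absent from this model only.
- That the tested result is off by as much as 0.15 SD. That figure belongs to a T4 arm difference, which Section 14.0 does not test, and to 20% loss before T2, whereas the plan assumes 10% during intervention.
- That bias is expected. No figure in the documents supports dropout that differs by arm. If correlations are equal across visits, as a random caregiver intercept implies, the arm-by-time term is unbiased even under the dropout patterns above.

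What does not stand is that the restriction is needed. A T2-T4 contrast can be taken from a model that includes T1, and comparing attrition rates describes selective dropout without adjusting for it.

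**Conclusion.** The point holds as a defect of specification with a conditional and modest numerical effect. The maintenance model omits caregivers who leave the study before T2 (about 24 of 240 at the plan's rate, 48 at most under its overall allowance), does not use their T1 scores, and leaves the T1-T4 arm difference without a primary analysis.

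Under the assumed arm-dependent dropout, the tested T2-T4 arm-by-time term is biased by about 0 to 0.04 SD at about 10% loss and 0 to 0.07 SD at about 20%. A T4 arm difference from the same data would be biased by about 0.02 to 0.08 SD and 0.04 to 0.15 SD respectively. These ranges rest on the assumed correlations and dropout slopes. The bias is proportional to D, so steeper dependence on baseline would give more, and identical dropout in the two arms gives none. The plan should be changed, but its maintenance result cannot be called invalid on this ground.

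**What to change.** In Section 14.0 (Aim 1, Primary Analyses), replace the T2-T4 restriction with one longitudinal model per primary outcome:

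- fitted to all randomized caregivers with any T1-T4 data;
- with categorical time (T1, T2, T3, T4), arm, arm-by-time, and the site term as now;
- with an unstructured within-caregiver covariance in place of the random caregiver intercept alone.

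Report the T2-T4 arm difference in change and the T1-T4 arm difference as contrasts. Use the same model for caregiver secondary outcomes and Aim 3, which already refers back to this framework.

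The cost is SAP wording; no new data are needed. Four visits need 4 × 5/2 = 10 covariance parameters. If the eight weekly HADS assessments are added, 12 occasions would need 12 × 13/2 = 78, so those rows call for a more parsimonious structure, stated in advance. The model corrects only for dropout related to observed scores. Dropout driven by unobserved distress would still need a sensitivity analysis.

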Rumination and Worry (Pre to Post) and Patient Outcomes: For rumination and worry pre to post intervention, only 2 assessments (T1 and T2) are collected. Patient outcomes are only collected at baseline (T1) and 3-months post-treatment (T3). Rather than test for a time-treatment interaction effect, differential change will simply be tested as the main group (ERT-C vs. CBT-C) effect in an HLM model of change scores regressed on this main effect and with a random per-site intercept, separately for each outcome (i.e., caregiver rumination, caregiver worry, patient outcomes).

Exploratory Analysis - Potential Moderators: As we move into the era of precision medicine and person-centered mental health care,[197] it is necessary to examine caregiver-specific factors that may moderate impact of ERT-C so that we may build a foundation for a targeted approach to addressing caregiver anxiety and depression. The impact of moderators of psychosocial interventions among patients with cancer has received increasing attention[198], with growing evidence for the influence of age and cancer type on various psychosocial outcomes. Therefore, putative moderators of therapeutic efficacy, including cancer site, cancer stage, and caregiver sociodemographic factors, will be assessed within this same HLM framework for Aim 1. Longitudinal change scores for each outcome at each major time point (i.e., T2, T3, T4) will first be calculated. Next, potential moderators will be included in separate HLM models, where each model regresses the change score on main effects for ERT-C and the moderator, plus an interaction of the two. The HLM structure will account for clustering effects of the sites only, as change scores are assessed individually and thus a single observation per participant.

Attrition and Missing Data. We computed sample size estimates anticipating 20% attrition. Based on previous trials at MSK and MGH with caregivers, missing data should be less than 20% by T3. Missing data rates and attrition will be compared between treatment arms, and also by pre-intervention measures.

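### Worry and rumination (T1 to T2) and all patient outcomes are tested with change scores not adjusted for baseline, which gives up precision that the T1 score already collected would provide

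*Combined protocol and SAP*

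**What the plan says.** Section 14.0 (Rumination and Worry (Pre to Post) and Patient Outcomes) sets these outcomes apart because each has two assessments: "For rumination and worry pre to post intervention, only 2 assessments (T1 and T2) are collected", while patients are assessed at T1 and T3 alone. For all of them, "differential change will simply be tested as the main group (ERT-C vs. CBT-C) effect in an HLM model of change scores". The only other term in the model is a random intercept for site, and each outcome is modelled on its own. No baseline covariate is named.

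Worry and rumination are two of the four primary outcomes. The superiority rule at the end of the Aim 1 primary analyses in section 14.0 requires a significant T1 to T2 difference, so for these two outcomes the change-score test is a required step. The T2 to T4 maintenance analysis uses the longitudinal mixed model and is not affected.

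For the HADS outcomes the longitudinal model also covers T1 to T2. It contains an arm indicator, and "baseline assessments will be included as an outcome and not a covariate". As written, that leaves the arms free to differ at T1.

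**The concern.** A change score is a regression on baseline with the slope fixed at 1. When the pre-post correlation is below 1, that slope is too steep: baseline noise is carried into the outcome, and a chance imbalance at T1 is over-corrected. Estimating the slope removes this excess and uses a measurement that every participant is already scheduled to give.

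At stake is power for two primary outcomes, and for a patient aim in which the plan expects 120 patients enrolled and 96 retained. The choice should be settled before unblinded data are seen, because choosing between a change score and a baseline-adjusted model afterwards would be data-driven.

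**Working it through.** **Inputs.** From section 14.0 (Power and Sample Size for Aim 1):
- Worry and rumination: 240 caregivers, 10% attrition, so 216 or 108 per arm; alpha 0.0125; d=0.50 at 80% power.
- Patients: 120 enrolled, 80% retained, so 96 or 48 per arm; alpha 0.05; d=0.63 at 80% power, using a t-test on change scores.

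Sidedness is not stated; two-sided is assumed. The only within-subject correlation given is an ICC of 0.2, stated for the mixed-model power simulation for depression and anxiety.

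**The plan's own figures.** With d in SDs of the analysed variable:
- 108 per arm, alpha 0.0125, d=0.50: power 88.0% (normal) or 87.5% (t). The detectable d at 80% power is 0.45 to 0.46.
- 48 per arm, alpha 0.05, d=0.63: power 87.0% (normal) or 86.3% (t). The detectable d is 0.57 to 0.58.

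The stated 80% figures are therefore conservative on this reading. Both reproduce if d is in raw-score SDs and r=0.4, because the change-score variance is then 2(1-0.4)=1.2. The detectable effects become 0.50 and 0.63. The documents do not state that assumption.

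**Variance.** Take equal variances (1) at both times and correlation r.
- Change score: 2(1-r).
- Adjusted for T1: 1-r².
- Ratio: (1-r²)/[2(1-r)] = (1+r)/2, below 1 for every r<1.

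Simulation with N=240 and 10% missing at random gave ratios of 0.60, 0.72, 0.76 and 0.86 at r=0.2, 0.4, 0.5 and 0.7, against 0.60, 0.70, 0.75 and 0.85 from the formula. Both estimators were unbiased.

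**Power and detectable effect, raw-score SDs, normal approximation.** With v the variance above:
- Worry and rumination: SE = √(2v/108); power = Φ(0.50/SE − 2.498).
- Patients: detectable effect = (1.960+0.842)·√(2/48)·√v = 0.572·√v.

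Example at r=0.4:
- Change score: SE = √(2×1.2/108) = 0.149; 0.50/0.149 = 3.354; power = Φ(0.856) = 80.4%.
- Adjusted: SE = √(2×0.84/108) = 0.125; 0.50/SE = 4.009; power = Φ(1.511) = 93.5%.

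| r | Variance ratio | Worry/rumination power: change → adjusted | Patient detectable effect: change → adjusted |
|---|---|---|---|
| 0.2 | 0.60 | 65.8% → 89.5% | 0.72 → 0.56 |
| 0.4 | 0.70 | 80.4% → 93.5% | 0.63 → 0.52 |
| 0.5 | 0.75 | 88.0% → 96.0% | 0.57 → 0.50 |
| 0.7 | 0.85 | 98.8% → 99.6% | 0.44 → 0.41 |
| 0.8 | 0.90 | both above 99.9% | 0.36 → 0.34 |

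If d is instead in change-score SDs, then over r=0.2 to 0.8 (t-based) adjusted power is 98.6% down to 91.1% for worry and rumination, against 87.5%. For patients it is 97.6% down to 89.6%, against 86.3%.

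**HADS, T1 to T2.** Section 14.0 expects 10 assessments but does not fix the time coding. With linear, equally spaced time, compound symmetry and complete data, holding the arms equal at T1 reduces the variance of the time-by-arm term to 0.59 of its value at ICC 0.2, 0.82 at ICC 0.5 and 0.91 at ICC 0.7.

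**The case against.** The strongest reply is that the plan is sound on its own terms. The change-score test is unbiased under randomization with data missing completely at random, and it does not inflate type I error. With d read in change-score SDs, the stated sample sizes exceed 80% power. The ICC of 0.2, where the gain is largest, belongs to another calculation. The PSWQ is described in section 9.0 as a trait measure, for which a low pre-post correlation is not the obvious choice, and at r=0.7 or 0.8 the power gain is small. All of this stands and limits the size of the point. It does not remove the gain, which exists for any r below 1.

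A reader might go further and infer that change scores wrongly discard participants whom baseline adjustment would keep. Section 13.2 does say "Participants need to only complete the baseline assessment for the data to be considered evaluable", and by the plan's rates about 24 of 240 caregivers and 24 of 120 patients would have no follow-up score. But complete-case regression of T2 on T1 excludes the same people. A longitudinal model with equal baseline means keeps them formally, yet with two time points those seen only at baseline add almost nothing to the arm contrast. Being evaluable also does not promise a contribution to every test.

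**Conclusion.** The point holds as a free improvement in precision. The variance saving runs from 40% at r=0.2 to 10% at r=0.8. It rests on equal variances at the two times and on an assumed r. The value r=0.4, under which both of the plan's 80% figures reproduce, is a useful anchor but only an inference; it gives a saving of 30%.

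Three stronger readings are not supported. The documents do not show these tests to be underpowered against their stated targets. The change-score test is not biased and has no type I error fault. Baseline adjustment does not solve attrition. The random intercept for two sites is a minor matter, with no effect on the arm estimate shown; it is worth tidying because site is the randomization stratum.

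**What to change.** In section 14.0 (Rumination and Worry (Pre to Post) and Patient Outcomes), replace the change-score model with T2 (T3 for patients) regressed on arm, the T1 score and site as a fixed effect. In the HADS T1 to T2 model, constrain the arm means to be equal at T1 and state the time coding.

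In the power section, state the SD scale and the pre-post correlation behind d=0.50 and d=0.63.

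Address missing follow-up separately. Section 14.0 only compares missingness rates between arms and by pre-intervention measures. T3 and T4 data from caregivers who missed T2 could add information; patient outcomes need imputation or missing-not-at-random sensitivity analyses.

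The precision change costs SAP wording only: no new data, no participant burden and no change in sample size. It should be made before any unblinded analysis.
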